After downloading data, each participant will be visited to complete a 24-hour dietary recall about Thursday, which will be conducted for Thursday using the Nutrition Data System for Research (NDS-R; Nutrition Coordinating Center, University of Minnesota, Minneapolis, MN). The child will be asked to use their diary and food guide to help facilitate the recall; the RA will go through the diary and recall with the child. [See 24-hr Diet Recall Protocol]. During this visit, you will have the opportunity to show the child how to use the food guide. Also, you will help mothers select a bedtime and wakeup time for the following weeks. Write this down on the front page of the *Sleep and Food Diary*, and on the *Telephone/Texting Contact Form*. At the end of the visit, families will be given a \$25 gift card in appreciation of their time and participation. Before leaving, ask when would be a good time to call on Saturday.

Saturday (Phone call)

The RA will call the child on Saturday to complete a 24-hour dietary recall about Friday. Follow the same protocol as on Friday. After this you can remind the child that he/she is free to remove the accelerometer until Tuesday (unless they are being asked to re-wear), and that you will be making a reminder phone call on Tuesday.

Week 2

Children will be randomized into one of two sleep conditions: long (healthy) sleep or short (restricted) sleep. Participants have already been pre-assigned an ID number and random assignment has been predetermined in order to have an equal number of boys and girls in each condition. [See Participant Randomized Sleep Schedule.] On Tuesday mid-morning, mothers

will be called to notify them regarding which sleep schedule their child will follow in Week 2. You will remind parents of the set bedtime and waking time for both conditions to make sure that their child complies with the sleep schedule. This information should be written on the front page of the *Sleep and Food Diary*, and on the *Telephone/Texting Contact Form*. Children will follow the sleep schedule from Tuesday to Friday night (ending on Saturday).

For the long sleep condition, children will be asked to sleep ≥ 10.5 hrs.

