For the short sleep condition, children will be asked to sleep < 8 hrs. If parents are concerned regarding this sleep schedule, you should acknowledge their concern. Remind them that this was discussed in the study consent form, and that you will be monitoring their child for daytime drowsiness, which is a possible side effect. It is ok for their child to nap. Also, reassure them that you will be monitoring their child and calling them to make sure that they are not experiencing too much daytime drowsiness.

Child-mother pairs will continue to receive 2 daily texts or phone calls (Wednesday-Friday) as a reminder to wear the accelerometer, to complete sleep and food diaries, and to remind them of their bedtime and wake up time (as discussed).

Children in the Short Sleep Condition will be called and asked to complete the Pediatric Daytime Drowsiness Scale (Thursday). You will calculate their drowsiness score and discuss with [name] if the score is 13 or higher. The parent will also be advised. Encourage their child to take naps and that this part of the study is almost complete. If they wish to withdraw from the study, then that is ok, as their participation is voluntary.

Friday (Third home visit)

Children will be visited on Friday. Make sure that the child has the diary and food guide. Have him/her remove the accelerometer and download the accelerometer data. Check for compliance and accelerometer charge. If child is missing one day, then ask him/her to keep the accelerometer on until Sunday at noon. If they did not comply the whole week then ask them to repeat the week. If they do not want to re-wear and decide to withdraw, then thank them for their time.

After checking accelerometer compliance, you will perform a 24-hour dietary recall about Thursday. Once again, you will use the diary and the food guide. Upon completion of the visit, the family will be given a \$25 gift card for their time and participation in Week 2. Before leaving, ask when would be a good time to call on Saturday.

Saturday (Phone call)

Child participant will receive a phone call on Saturday and asked to complete a 24-hour dietary recall about Friday. Follow the same protocol as on Friday, using the diary and food guide. After this you can remind the child that he/she is free to remove the accelerometer until Tuesday (unless they are being asked to re-wear), and that you will be making a phone call on Tuesday as a reminder.

A 3-night period between sleep conditions will follow.

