Title: Sleep duration and risk for obesity in Mexican American children

Number: NCT03947918

Document date: June 16, 2020

PI: [name] (1 K01 HL129087)

Subject: Analysis plan

Analysis includes using 2-way repeated measures ANOVA. First, I will test for order effects (8 hr condition assigned first versus second) including the order main effect and the sleep-condition-by-order interaction. Non-significant order effects will be dropped and the model refit, as appropriate. If some order effects are retained in the model, then I will perform custom contrasts within each order condition, e.g., 8 v. 10.5 hrs within each order condition; and across order conditions, e.g., 8 hrs in the 8-hr-first condition versus 8 hrs in the 10.5-hr-first condition. These models will mostly focus on differences between sleep conditions.

I can use the usual sleep condition to categorize children in terms of the regular sleep duration, which can be used as either as a continuous or a categorical (e.g.,  $\leq 9$  v.  $> 9$  hrs) covariate in the regression models. This would allow testing the interaction between usual sleep duration (whether categorical or continuous) and assigned sleep duration (8 v. 10.5 hrs). If order effects are operating, i.e., significant condition-by-order interaction, then I will test 3-way interactions: condition-by-order-by-X, where X is a variable derived from the regular sleep condition, i.e., either continuous covariate or binary.

I will average Thursday and Friday dietary intake (e.g., caloric intake) and PA within week 2 and week 3, using week 1 dietary intake and PA as covariates. I will also test all 4 assessments of dietary intake and PA (Thursday and Wednesday for week 2 and week 3) in a single repeated measures model, using week 1 assessments (Thursday and Friday) as covariates. Time can be treated as a continuous or categorical variable (week 2-Wed.; week 2-Thurs; week 3-Wed.; week 3-Thurs). If categorical, I can then compare dietary intake and PA within each day of the week (e.g., Wed. and Thurs.) within each assigned sleep condition.

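### When the condition-by-order interaction is retained, the SAP's 8 v. 10.5 hr contrasts within each order mix the sleep effect with the Week 2 to Week 3 shift

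*SAP*

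**What the plan says.** The Protocol (Study Overview, Week 2, Week 3) describes a two-condition, two-week crossover. Each child is randomised to short or long sleep in Week 2 and takes the other in Week 3, after a 3-night gap. On allocation it says that "random assignment has been predetermined in order to have an equal number of boys and girls in each condition"; the number of children per order is not given.

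The SAP (paragraph 1) fits a two-way repeated measures ANOVA and tests the order main effect and the condition-by-order interaction. Then:

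- For terms that do not reach significance: "Non-significant order effects will be dropped and the model refit, as appropriate".
- For the branch where at least one such term stays, with 8 v. 10.5 hours as the named example: "If some order effects are retained in the model, then I will perform custom contrasts within each order condition".
- It also plans a comparison across orders: "8 hrs in the 8-hr-first condition versus 8 hrs in the 10.5-hr-first condition".
- On which estimate answers the sleep question, it says only: "These models will mostly focus on differences between sleep conditions".

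Paragraph 2 proposes usual sleep duration as a moderator: "This would allow testing the interaction between usual sleep duration (whether categorical or continuous) and assigned sleep duration". It adds a conditional step: "If order effects are operating, i.e., significant condition-by-order interaction, then I will test 3-way interactions: condition-by-order-by-X".

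**The concern.** With two conditions, two weeks and two orders, knowing a child's order and current condition tells you the week. The condition-by-order term is therefore the week term under another name. The SAP calls a significant interaction an order effect and responds by splitting the 8 v. 10.5 comparison by order. It does not say that the term is week plus carryover, or which estimate is the sleep result once the term is kept.

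A sleep effect that is the same in both orders could then be reported as present in one order only, and a null effect could appear as a significant difference.

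Some differences between the weeks are built into the Protocol. On the Week 2 Friday there is a home visit with a compliance check and possible extended wear: "After checking accelerometer compliance, you will perform a 24-hour dietary recall about Thursday". In Week 3 Friday is a phone call, and the accelerometer data are uploaded only on Saturday. The Thursday recall is thus in person in Week 2 and by phone in Week 3, and the Friday recall the reverse. Recall mode may cancel in the planned Thursday-Friday average, but not in single-day comparisons. The documents do not give the size of any week shift.

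**Working it through.** **Inputs.** The design is from the Protocol and the contrasts are from the SAP. Neither document states a sample size, alpha, SD or effect size, so there is no planned figure to reproduce.

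**Notation.** S = sleep effect (8 minus 10.5 hrs); W = Week 3 minus Week 2 shift; C8 and C10.5 = carryover into Week 3 from each condition; a and b = baseline levels of the two order groups, equal in expectation under randomisation.

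| Order | Week 2 | Week 3 |
|---|---|---|
| 8 first | a + S (8 hrs) | a + W + C8 (10.5 hrs) |
| 10.5 first | b (10.5 hrs) | b + S + W + C10.5 (8 hrs) |

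**Step 1: what each planned quantity estimates.**

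- 8 minus 10.5 in 8-first children: S - W - C8.
- 8 minus 10.5 in 10.5-first children: S + W + C10.5.
- Interaction (first minus second): -2W - (C8 + C10.5). S cancels.
- Equally weighted average of the two: S + (C10.5 - C8)/2. W cancels.
- 8 v. 8 across orders: (a - b) - W - C10.5. It contains no S and is a between-child comparison.
- Order main effect: (a - b) + (C8 - C10.5)/2.

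Example: S = W = 0.3 and no carryover give contrasts of 0.3 - 0.3 = 0 and 0.3 + 0.3 = 0.6, with average 0.3. With C8 = 0.07 and C10.5 = 0.04 they are -0.07 and 0.64. Their average is 0.285 = 0.3 + (0.04 - 0.07)/2, and the 8 v. 8 contrast is -(0.3 + 0.04) = -0.34.

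**Step 2: same model, different label.** Over the four cells, {intercept, condition, order, condition-by-order} has rank 4, and adding week leaves the rank at 4. The unreduced SAP model already spans week. Likewise condition-by-order-by-X equals week-by-X up to sign in every cell. The three-way test is therefore week-by-X, plus any carryover-by-X, and not moderation of the sleep effect.

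**Step 3: precision.** If the within-child difference has SD 1 and orders are equal, a within-order contrast has standard error 1/√(N/2) and the average has 1/√N. The ratio is √2, about 1.4.

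**Step 4: size.** Assumptions: N = 30 to 80 children, equal orders, two-sided 0.05, no carryover, shifts in SD of the within-child difference, 40,000 simulated trials per cell. The interaction was tested by two-sample t-test and the within-order contrasts by paired t-test.

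S = 0.3 in both orders: chance that the interaction is significant and exactly one order shows a significant contrast.

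| W | 0 | 0.1 | 0.2 | 0.3 | 0.5 |
|---|---|---|---|---|---|
| N = 30 | 4% | 7% | 16% | 31% | 62% |
| N = 50 | 5% | 10% | 27% | 51% | 77% |
| N = 80 | 5% | 14% | 41% | 72% | 76% |

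This does not need W to equal S: with S = 0.5 and N = 50, W = 0/0.2/0.3/0.5 gives 4/27/53/90%.

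S = 0: chance that the interaction and at least one within-order contrast are significant.

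| W | 0 | 0.1 | 0.2 | 0.3 | 0.5 |
|---|---|---|---|---|---|
| N = 30 | 3% | 6% | 13% | 26% | 64% |
| N = 50 | 3% | 7% | 21% | 44% | 88% |
| N = 80 | 3% | 10% | 33% | 66% | 98% |

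The week-adjusted condition effect rejects in about 5% throughout.

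**Step 5: limits of the week-adjusted effect.** With N = 50, S = W = 0, C10.5 = 0 and C8 = 0.1/0.2/0.3, it is off by half the carryover difference (0.05/0.10/0.15 SD in size) and rejects in 6/10/18%. With equal carryover of 0.2 it rejects in 5%, while the interaction is significant in 28%.

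**Step 6: dropping the interaction.** With equal orders there is no bias and error stays near 5%. At an assumed 30/20 split the refitted effect is (30(S - W) + 20(S + W))/50 = S - 0.2W, which is 0.06 SD off at W = 0.3. The error rate of the test-and-drop rule is then 5.3 to 5.8%.

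**The case against.** **The SAP does not call the within-order contrasts the sleep result.** The retained model still holds the condition main effect, which, equally weighted, is the estimate recommended here. No term is missing. That stands, and it limits the harm to the branch where the interaction is retained and the split contrasts are read as sleep effects. But planning 8 v. 10.5 separately by order invites that reading, and nothing in the SAP warns against it.

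**Paragraph 3 of the SAP has a time factor that separates the weeks.** With condition in that four-assessment model and time categorical, week is adjusted for. This helps only in part: the factor is optional, may be continuous, and is not tied to the order tests. It cannot unconfound the within-order contrasts, because week and condition-by-order are the same column. Nor can the Week 1 covariates, which are constant within a child and cancel in these contrasts.

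**The percentages largely restate an assumed week shift.** True. At N = 50 and S = 0.3, the interaction alone is significant in 5/11/28/55% for W = 0 to 0.3, close to the joint figures. At W = 0 the joint rates are only 3 to 5%. The tables show what can happen, not how likely it is. The algebra does not depend on them.

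**Test-and-drop does little damage.** Also true, by Step 6. Keeping week in the model is the cleaner practice rather than the repair of a demonstrated bias.

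**The remedy assumes equal carryover.** It does, and Step 5 shows the cost when that fails. If only the order main effect is retained, the week problem does not arise, since both orders give one common condition effect (apart from the 0.2W shift at a 30/20 split). But that main effect carries (C8 - C10.5)/2, exactly minus the bias in the recommended estimate, so its retention is not reassuring about carryover.

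**Conclusion.** The point holds and should be fixed. When the condition-by-order interaction is retained, the two planned 8 v. 10.5 contrasts estimate S - W - C8 and S + W + C10.5, and neither is a sleep effect unless the week shift and carryover are nil. This is exact for the design in the Protocol and needs no assumed number. The follow-up three-way test inherits the same problem.

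How often it would mislead depends on N, alpha and the week shift, none of which is documented. At N = 50 and an assumed shift of 0.3 SD, the chance is about 51% that a common effect of 0.3 SD appears in one order only, and 44% that a null effect yields a significant within-order contrast, in each case together with a significant interaction. With no week shift these chances are about 5% and 3%. The condition main effect itself remains sound if carryover is equal.

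**What to change.** 1. Keep condition, order and week in every model, without testing and dropping. This is the SAP's unreduced model with the interaction relabelled as week plus mean carryover.
2. Name the equally weighted, week-adjusted condition effect as the sleep result. State that it estimates S + (C10.5 - C8)/2 and so assumes equal carryover after the two conditions. Report the order main effect alongside it as the term that bears on this assumption. It is a between-child comparison, and a non-significant result does not show that carryover is equal.
3. Label the within-order 8 v. 10.5 contrasts and the across-order 8 v. 8 contrast as descriptive and confounded with week.
4. Base moderation by usual sleep on the condition-by-X term already planned, with week-by-X always included. Do not read the three-way term as moderation of the sleep effect.
5. Optional sensitivity analysis: 8 v. 10.5 between orders in Week 2 only, which is free of week and carryover. Its standard error is √(2/(1 - ρ)) times that of the main estimate, that is 1.7 to 2.6 times for an assumed within-child correlation ρ of 0.3 to 0.7, before covariate adjustment.

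The cost is SAP wording and one degree of freedom for week. No new data are needed.

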[figure not shown]
Title: Sleep duration and risk for obesity in Mexican American children

Number: NCT03947918

Document date: June 3, 2019

PI: [name] (1 K01 HL129087)

Subject: Study protocol

STUDY OVERVIEW

The Summertime: Kids in Motion study is a 3-week study of Mexican American children in the San Francisco area. This study includes six home visits, with the intention of making this study convenient for participants and increase study completion. The RA will make 2 home visits (Monday, Friday) and 1 phone call (Saturday) in Week 1; 1 visit (Friday) and 1 phone call (Saturday) in Week 2; and 1 phone call (Friday) and a final visit (Saturday) in Week 3. In Week 1, children will continue their normal activities. In Week 2, children will be randomized to follow a short (restricted) sleep or long (healthy) sleep schedule. In Week 3, children will be asked to follow the sleep schedule opposite from Week 2. Behavioral assessments over the three weeks will include sleep duration for (Tuesday night-Friday night), physical activity and sedentary behavior (Wednesday-Friday), and dietary intake (Thursday and Friday). A full description is provided below.

STUDY PROCEDURES AND DATA COLLECTION

Recruitment

Recruitment is critical to the study. Participants will be recruited from the community, such as community organizations, youth summer programs, churches, swat meets, parks, and UCSF clinics. Community organizations may be best to recruit from during the week, whereas parks and churches may be the best during the weekend.

When recruiting from any community organization, it will be important to contact them ahead of time over the phone. When going out into to make the initial contact, always have your SFSU student ID or UCSF badge with you and introduce yourself as a research assistant working [name], a researcher at the Univ. of California, San Francisco. You will then describe the study—a study examining how circadian behaviors such as sleep is related to physical activity and eating patterns—and that you are recruiting families with 8-10-year-old Mexican American/Mexican children. Describe the study protocol in short, and that this is a 3-week study. If the organization contact is willing to allow you to recruit participants from that location, then ask when would be the best time to catch parents so that you can speak with them and provide them with study information to participate.

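### The SAP names no short v. long sleep contrast that is free of both week and carryover effects; the Week 2 comparison adjusted for Week 1 would be one and should be fixed in advance as a sensitivity analysis

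*SAP*

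**What the plan says.** The Protocol's Study Overview sets out a two-period crossover with a lead-in week:

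- Week 1: "In Week 1, children will continue their normal activities".
- Week 2: "In Week 2, children will be randomized to follow a short (restricted) sleep or long (healthy) sleep schedule".
- Week 3: "In Week 3, children will be asked to follow the sleep schedule opposite from Week 2".

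Under Week 2, Saturday (Phone call), the Protocol gives the gap: "A 3-night period between sleep conditions will follow".

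The first paragraph of the SAP specifies a two-way repeated measures ANOVA and begins with a test of order effects, "including the order main effect and the sleep-condition-by-order interaction". It then says: "Non-significant order effects will be dropped and the model refit, as appropriate". If some order effects stay in the model, custom contrasts follow, introduced as examples. Within orders the example is "8 v. 10.5 hrs within each order condition"; across orders it is "8 hrs in the 8-hr-first condition versus 8 hrs in the 10.5-hr-first condition".

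The third paragraph of the SAP describes two outcome models, one on weekly averages and one on four daily assessments. Both use Week 2 and Week 3 outcomes together with Week 1 values as covariates. Neither document names a short v. long comparison confined to Week 2.

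**The concern.** Each named short v. long contrast uses Week 3, which begins three nights after the opposite schedule. The named across-order contrast has the same sleep condition on both sides. So whichever way the order tests fall, the plan names no sleep effect that is protected from both week and carryover. The gap matters most when order effects are retained, because the analyst then already has reason to doubt the pooled result and most needs a clean alternative.

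The design can supply one. Week 2 is a parallel randomised comparison, nothing assigned precedes it, and Week 1 gives a pre-assignment value of the same outcomes. If this contrast is chosen only after the order tests are seen, it becomes a data-dependent choice.

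**Working it through.** The plan states no sample size, alpha, SD, correlation or effect size, so it has no figure to reproduce. The first two steps are algebra and need no numbers. The rest uses assumed values.

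**1. Cell means.** Let τ = short minus long, π = Week 3 minus Week 2, and λS, λL = carryover into Week 3 from short and long sleep.

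| Order | Week 2 | Week 3 |
|---|---|---|
| 8-hr first | μ + τ | μ + π + λS |
| 10.5-hr first | μ | μ + τ + π + λL |

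**2. What each contrast estimates.**

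| Contrast | Expectation | In the SAP? |
|---|---|---|
| Pooled condition effect, equal numbers per order | τ − (λS − λL)/2 | yes |
| 8 v. 10.5 within 8-hr first | τ − π − λS | named |
| 8 v. 10.5 within 10.5-hr first | τ + π + λL | named |
| 8 v. 8 across orders | −π − λL | named |
| Order main effect | (λS − λL)/2 | tested |
| Condition-by-order interaction | −2π − λS − λL | tested |
| Week 2 short v. long | τ | not named |

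The pooled effect is biased only by differential carryover. The 8 v. 8 contrast does not contain τ. The interaction responds to week and to the sum of the carryovers, so it cannot isolate the difference that causes the bias.

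A simulation with 20,000 children per order (τ = 0.4 SD, π = 0.1, λL = 0, correlation 0.5) agrees. With λS = 0, 0.1, 0.2 and 0.4, the pooled estimate is 0.41, 0.34, 0.30 and 0.19, and the Week 2 ANCOVA gives 0.42, 0.39, 0.40 and 0.40.

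**3. Size in an assumed case.** Outcome SD 1, n = 40 in total (20 per order), between-week correlation r = 0.5, λS = 0.5, λL = 0, π = 0, τ = 0. Rejection rates are from the noncentral t, two-sided 5%.

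- Pooled bias: 0.5/2 = 0.25 SD in absolute size.
- Pooled SE: √(2(1−r)/n) = √(1/40) = 0.158. The ratio is 0.25/0.158 = 1.58, and the test rejects in 34% of trials. This is the rate for the pooled test itself, before any selection by the order tests.
- Order main effect, tested on the sum of the two weeks: SE = √(2(1+r)·4/n) = √0.30 = 0.548, expected difference 0.5, power 14%.
- The same test adjusted for Week 1: SE = √((2(1+r) − 4r²)·4/n) = √0.20 = 0.447, power 19%.
- Interaction: SE = √(2(1−r)·4/n) = √0.10 = 0.316, expected size 0.5, power 34%.
- At least one of the two order tests: the sum and the difference of the two weeks are independent here, so 1 − (1 − 0.144)(1 − 0.338) = 43%.

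**4. Range.** Over n 30-60, r 0.3-0.7 and differential carryover 0.25-0.5 SD, the false-positive rate of the pooled test runs from 9% to 69%. Order main-effect power runs from 6% to 22% unadjusted and from 7% to 35% adjusted for Week 1.

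**5. Precision of the Week 2 contrast.** The ANCOVA SE is √((1−r²)·4/n) = √0.075 = 0.274 in the assumed case. Its ratio to the pooled SE is √(2(1+r)): 1.61, 1.73 and 1.84 for r = 0.3, 0.5 and 0.7.

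**The case against.** Several points on the other side are sound.

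- **Detection.** A reader might infer that no planned result could reveal carryover. That is too strong. Two order tests are planned, and in the assumed case at least one is significant in about 43% of trials. But the interaction, which supplies much of that, also fires on a plain week effect, and a significant result leads only to the contrasts discussed above.
- **Overlap with the order test.** Write D2 and D3 for the short-minus-long difference in Weeks 2 and 3. The pooled estimate is (D2 + D3)/2, so the gap between the Week 2 and pooled estimates is (D2 − D3)/2, which is the order main effect. With Week 1 adjustment the two are almost the same (simulated correlation 0.99). Showing the estimates side by side therefore adds almost no power to detect carryover. What it adds is a stand-alone unbiased estimate of sleep.
- **Imprecision.** With SE 0.274, the 95% interval is about ±0.55 SD, too wide to expose a bias of 0.25 SD. In the assumed case the pooled estimate has the smaller mean squared error while differential carryover is below 2√(0.075 − 0.025) = 0.45 SD. This is why the within-child estimate should stay the main result.
- **Plausibility.** The 34% case pairs no sleep effect during the schedule with a 0.5 SD residual effect the week after, and the documents support neither. Outcomes are also measured later than the three-night gap suggests. Counting from the end of the Week 2 schedule, Wednesday activity follows four nights (three free, one on the new schedule) and Thursday intake follows five.
- **Open list.** The contrasts are only examples, and Week 2 short v. long is itself an across-order contrast that the model's cell means could yield. The supportable wording is that it is not named, not that it is excluded.
- **The 8 v. 8 contrast.** It is a reasonable order diagnostic, and the SAP does not present it as a sleep estimate. It need not be removed.

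**Conclusion.** The point holds as a cheap improvement to the plan. The structural part rests on algebra alone: with order terms retained, the named contrasts either confound sleep with week and carryover or contain no sleep effect; with order terms dropped, the pooled estimate carries half of any differential carryover. Among comparisons of the randomised groups, only Week 2 short v. long is free of both week and carryover.

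The size rests on assumptions that the documents neither give nor contradict: in the case of 40 children, correlation 0.5 and differential carryover 0.5 SD, about 34% false positives, against 14-19% power for the order main-effect test.

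A reader might go further and infer that the trial's sleep estimates are biased. The documents do not support that. Nothing in them shows that carryover exists, and equal carryover from the two schedules leaves the pooled estimate unbiased.

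**What to change.** In the first paragraph of the SAP, add a pre-specified sensitivity analysis for each outcome, reported whatever the order tests show. It compares the Week 2 outcome in the short condition (8-hr-first order) with the long condition (10.5-hr-first order), by ANCOVA on the Week 1 value of the same outcome. Present it beside the week-adjusted within-child estimate, which remains the main result. Do not make either analysis conditional on a significant order test. If the 8 v. 8 contrast is kept, label it as an order diagnostic and not as a sleep estimate.

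The cost is one extra ANCOVA per outcome on data already collected. The SAP should state that this estimate has a standard error about 1.6-1.8 times that of the within-child one (for correlations of 0.3-0.7), and that agreement between the two does not demonstrate absence of carryover.

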each week (starting on Tuesday and ending on Saturday at noon), except when bathing or swimming. On Wednesday - Friday, children and mothers will be asked to complete a sleep and food diary for the child and to document times that the accelerometer is removed. Mother and child will be given a food reference guide (with illustrations of serving sizes of different foods) to assist them when completing the diary. A pen and accelerometer will be provided in a small box, and the diary, food guide, and accelerometer directions in a folder. Let them know that you will be contacting them through the week to remind them to wear the accelerometer and fill out diaries. Ask whether they prefer texts or phone calls and confirm the best number to be reached at. Lastly, ask them the best time to stop by on Friday for the next visit.

Texts and phone calls. Wednesday through Friday, mothers (and children if applicable) will receive two daily text messages (morning and evening) to remind children to wear the accelerometers and to complete the diaries.

Friday (Second home visit)

Upon arriving, greet the family and wait to be invited in. Make sure that the child has all the items such as the diary and food guide. First, you will have him/her remove the accelerometer and you will download the accelerometer data. Check to see that the child was compliant and that the accelerometer has 50% charge left. If child is missing one day, then ask him/her to keep the accelerometer until Sunday at noon. If they did not comply the whole week then ask them to repeat the week. If they do not want to repeat the week, then ask if they can re-wear it the following week. If they decide to withdraw, then thank them for their time as their participation is voluntary. Let them know that if they change their mind, they should call the number on the consent form.

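### The SAP's day-level model names Wednesday and Thursday as its days, which does not match the protocol's collection days: as written it omits Friday physical activity, and on either reading it uses four of six PA days

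*SAP*

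**What the plan says.** The protocol's Study Overview lists the weekly behavioural measures as "physical activity and sedentary behavior (Wednesday-Friday), and dietary intake (Thursday and Friday". The accelerometer is worn "each week (starting on Tuesday and ending on Saturday at noon), except when bathing or swimming" (Week 1, first home visit), so Friday lies inside the wear window. On the intervention, the Week 2 section says "Children will follow the sleep schedule from Tuesday to Friday night (ending on Saturday".

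The third paragraph of the SAP describes two analyses of diet and PA:

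- **Averaged analysis.** "I will average Thursday and Friday dietary intake (e.g., caloric intake) and PA within week 2 and week 3", with Week 1 values as covariates.
- **Day-level repeated-measures model.** "I will also test all 4 assessments of dietary intake and PA (Thursday and Wednesday for week 2 and week 3", "using week 1 assessments (Thursday and Friday) as covariates". If time is categorical, its levels are "week 2-Wed.; week 2-Thurs; week 3-Wed.; week 3-Thurs". A further example in the same paragraph again names Wednesday and Thursday.

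The SAP gives no reason for using different days in the two analyses. The paragraph treats diet and PA together and does not mention sedentary behaviour, which the protocol collects on the same days as PA.

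**The concern.** The day-level model is the only planned PA analysis with a time term, so it is the only one that could show how PA changes as assigned nights accumulate. As written it stops after two nights, although a listed PA day follows the third. It also presents four assessments as the complete set when six PA assessments are collected, and it adjusts for a baseline Friday that has no matching outcome day while its Wednesday outcome has no matching baseline.

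The wording does not fit diet either, because it asks for a Wednesday diet assessment that the protocol does not collect. Two analysts working from this paragraph could fit different models. At stake are a third of the PA days in this model and the ability to describe PA night by night over a short exposure.

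**Working it through.** **Inputs.** Collection days come from the protocol's Study Overview, assigned nights from its Week 2 section, and model days from the third paragraph of the SAP. Neither document gives a sample size, variance or effect size. The counts below do not need them.

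**1. The plan's own figure.** Wednesday and Thursday over two weeks: 2 × 2 = 4, as the SAP states.

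**2. Assessments collected in Weeks 2 and 3.** PA: 3 days × 2 weeks = 6. Diet: 2 days × 2 weeks = 4, on Thursday and Friday. So four is the full count for diet, though on different days from those named, and it is not the full count for PA.

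**3. Assigned nights before each PA day, counting from Tuesday night.** Wednesday 1, Thursday 2, Friday 3.

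**4. PA days used by each analysis.**

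| PA analysis | Days | Used of 6 | Omitted | Prior assigned nights (mean) |
|---|---|---|---|---|
| Average | Thu, Fri | 4 | Wed | 2-3 (2.5) |
| Day-level, as written | Wed, Thu | 4 | Fri | 1-2 (1.5) |
| Day-level, if the labels are a slip | Thu, Fri | 4 | Wed | 2-3 (2.5) |
| Day-level, all PA days | Wed, Thu, Fri | 6 | none | 1-3 (2.0) |

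Each analysis as planned leaves out 2/6 = 33% of the PA assessments. For diet, the day-level model as written has only Thursday available: 1 × 2 = 2 of the 4 assessments collected.

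**5. Baseline days.** The outcomes are Wednesday and Thursday and the covariates are Week 1 Thursday and Friday. Only Thursday appears in both.

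**6. Precision of a pooled condition effect, two versus three days per week.** Let r be the share of week-level variance common to days of the same week (assumed). The variance of a week's mean over k days is proportional to r + (1 − r)/k, and sample size cancels in the ratio:

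SE ratio = √{[r + (1 − r)/3] / [r + (1 − r)/2]}

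- r = 0: √(0.333/0.500) = 0.816, a reduction of 18%
- r = 0.3: √(0.533/0.650) = 0.906, a reduction of 9%
- r = 0.5: √(0.667/0.750) = 0.943, a reduction of 6%

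This is the gain from a third day of any kind, with the same effect on each day. It does not measure what Friday in particular adds.

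**The case against.** **Friday is analysed.** A reader might infer that the longest exposure is not modelled at all. The SAP does not support that: Friday PA is half of the Thursday-Friday average. Across the two analyses every PA day is used at least once. What is missing, as written, is Friday as a separate day in the model with a time term.

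**The labels may be a slip.** A reader might also infer that Friday was left out deliberately. There is good evidence the other way: the same sentence covers diet, which has no Wednesday recall; four is exactly the count for Thursday and Friday diet over two weeks; and the covariates are Thursday and Friday. Against this, the Wednesday-Thursday pairing appears three times. The documents do not settle it. If it is a slip, the Friday omission and the baseline mismatch disappear, but the model then omits Wednesday PA and still uses four of six days. Keeping PA on the same days as diet could be defended, but the SAP does not say that this is the intention.

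**Adding Wednesday may dilute the effect.** If the effect were proportional to prior nights (an assumption), adding Wednesday to a Thursday-Friday mean would cut the signal to 2.0/2.5 = 0.80. Signal relative to standard error would then be 0.80/0.816 = 0.98, 0.80/0.906 = 0.88 or 0.80/0.943 = 0.85 of its former value. This is a sound reason to leave the average alone. On the slip reading it also bears on a pooled effect from the day-level model, so the effect by day has to be shown. Against the model as written it points the other way, since mean prior nights rise from 1.5 to 2.0.

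**Friday is handled differently in the two weeks.** In Week 2 the monitor is removed and downloaded at a Friday home visit, while in Week 3 Friday is a phone call. That difference follows study week, not sleep condition, which is crossed over. The SAP does not give it as a reason to omit Friday.

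**Conclusion.** The point holds as a mismatch between the SAP's day labels and the protocol's collection schedule, and it should be corrected. As written, the day-level PA model omits both Fridays, the only listed PA days after three assigned nights, and its baseline days do not match its outcome days. If the labels are a slip, it omits both Wednesdays. On either reading it uses 4 of 6 PA assessments, and the same correction applies.

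The consequence is limited, because the condition comparison that includes Friday survives in the average. The documents contain nothing to show that the effect is largest on Friday; that would be an inference from the count of nights. Wear continues to Saturday noon, so some later accelerometer data may exist, but Saturday is not a listed outcome day. The 6-18% standard-error gain is illustrative: it depends on the assumed r of 0 to 0.5 and on an equal effect on each day. The 33% of PA days left unused depends on neither.

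**What to change.** State the days separately by outcome.

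- **PA and sedentary behaviour:** fit the day-level model to all six assessments (Wednesday, Thursday and Friday of Weeks 2 and 3), with day as a factor, a condition-by-day term, and Week 1 Wednesday-Friday values as the matching covariate.
- **Diet:** use the four Thursday and Friday assessments, with Week 1 Thursday and Friday as covariates.
- **Average:** keep the Thursday-Friday average unchanged.
- **Labels:** correct the list of time levels and the later day-of-week example to agree.

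The cost is SAP wording only, since the protocol already provides for these measurements. The downside is that Wednesday follows a single assigned night, so a pooled effect mixes one, two and three nights. Report the condition effect by day beside the pooled effect.
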